The primary endpoints will be the between group difference in change of dizziness related handicap and preferred gait velocity from baseline to 6 and 12 months follow up.

The study has two primary outcomes:

Dizziness-related handicap is measured using the Dizziness Handicap Inventory (DHI). The DHI is designed to quantify the perceived impact of dizziness and unsteadiness. It contains 25 questions, each item has 3 alternative scores “0” (no), “2” (sometimes) and “4” (yes), giving a score range of 0 to 100 DHI points (8).

Preferred gait velocity is used as a measure of functional level. The participants are asked to walk down an 8-meter pathway, timed in the middle 6 meters. The trial is timed using a stopwatch, from when the first foot passes the start point, to where the last foot passes the stop point. The mean velocity over two trials is calculated and presented in m/s.

A more detailed description of the study is presented in the protocol (1).

10. Randomisation and blinding.

After BI-VR the participants were block-randomised (in blocks of 16) into two groups, the CONTROL or TREATMENT group (Group A or B). Group allocations were performed using a random number generator and presented in a concealed envelope after completing the BI-VR. After breaking the code, the BI-VR therapist and the participants were aware of group allocation, while the assessor, also analysing the data, remained blinded. Prior to testing at 6- and 12-months participants were reminded not to divulge group allocation.

Prior to breaking the blinding, the authors of this SAP will agree on how to interpret the results on the bases of a blinded review of the data from the primary endpoints. Two possible interpretations will be made. One assuming that group A was in the treatment group, and the other assuming that group B was in the treatment group. When all authors have agreed to the interpretations, the randomisation code may be open. This procedure is conducted to reduce bias in the interpretation of the results.

11. Sample size calculation

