The sample size calculation was based on the between group difference in the mean change scores of the total DHI score and the preferred gait velocity. As two primary outcomes were chosen for the study power and sample size calculation was calculated for both outcomes (1). In order to obtain a clinically important group difference in the DHI of 11 points (9), with a significance level of 0.05 and a power of 80% (SD 18.95), 47 participants are required per group. In order to obtain a clinically important group difference in preferred gait velocity of 0.1 m/s (10, 11) with a significance level of 0.05 and a power of 80% (SD 0.15), 36 participants are required per group.

Therefore, the larger sample size of 47 in each group was used, resulting in at least 94 participants. To reduce the risk of dropouts affecting the analyses the preferred sample size was set to 124 participants, allowing for a conservatively estimated drop-out rate of 24%.

12. Description of hypothesis testing framework

All outcomes will be analyzed using a superiority framework, expecting that participants attending TREATMENT group will improve more than participants in the CONTROL group.

13. Planned interim analyses and stopping guidance

The published study protocol suggested possible interim analyses to adjust sample size. Apart from that no formal stopping guidelines or interim analyses were planned.

14. Details of timing of analyses

Participants were assessed at baseline, with follow-up testing after approximately 6 and 12 months. All analysis will be analysed after final data-collection. The primary outcomes will be analysed by a blinded biostatistician. The secondary outcomes will be analysed by LK. Data from baseline, 6- and 12-months follow-up will be included in these analyses. All primary and selected secondary outcomes presented at www.clinicaltrials.gov (NCT02655575) will be presented in the primary or subsequently secondary reports.

15. Timing of outcome assessments

Table 1. An overview of the different stages of the study, with a presentation of outcomes and their timepoint for testing.

Timepoint	STUDY PERIOD			
	Enrolment	Post-allocation		
	Month 0-2	Month 1-6	6 months	12 months
ENROLMENT				
Eligibility screen	X			
Informed consent	X			
Allocation		X		
INTERVENTIONS				
BI-VR		X		
VR-CBT/ Home exercises			X	
ASSESSMENTS				
Initial questionnaire and demographics	X			
Clinical dynamic visual acuity	X			
Grip strength	X			
PRIMARY OUTCOMES				

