Dizziness Handicap Inventory	X		X	X
Preferred gait velocity	X		X	X
SECONDARY OUTCOMES				
Physical tests				
Fast gait velocity	X		X	X
Elements from GPE	X		X	X
Dual task walking	X		X	X
Body sway	X		X	X
Head movement induced dizziness	X		X	X
Questionnaires				
Mobility Index, Alone	X		X	X
Body Sensation Questionnaire	X		X	X
Agoraphobic Cognition Questionnaire	X		X	X
Panic Attack Scale	X		X	X
Hospital Anxiety and Depression Scale	X		X	X
Vertigo Symptom Scale- Short form	X		X	X
Chalders fatigue questionnaire	X		X	X
EQ5D-5L	X		X	X
Subjective Health Complaints	X		X	X
Patient Global impression of Change			X	X

SECTION 4: STATICAL PRINCIPLES

Confidence intervals and p-values

16: Level of statistical significance and confidence intervals

All statistical tests carried out to assess the between-group effects, will consist of two-sided tests with a 95% confidence level ($p < 0.05$).

17: Adjustment for multiplicity

Since this study has two primary outcomes post-hoc analysis the Holm-Bonferroni method will be used to control for a possible Type 1 error.

18. Confidence intervals

All confidence intervals presented will be 95% and two-sided.

Adherence and protocol deviations

19.a. Definition of adherence to the intervention

Satisfactory adherence for the VR-CBT group was predefined as attending 6 of the 8 group treatment sessions (75%), and completion of at least 80% of the exercise diaries, where 100% was predefined as reporting exercising and following the walking program 5 times per week. Satisfactory compliance in the control group was predefined as completion of at least one phone call with the BI-VR therapist (1).

19.b. Description of how adherence will be presented

The adherence will be presented as the number and percentage of participants achieving satisfactory adherence (described above). For the intervention group the adherence to group attendance and home-exercises will be presented separately.

19c & 19d. Definition of protocol deviations and how they will be reported

Major deviations from adherence to protocol is defined as:

- Less than 50% attending more than 75% of the VR-CBT treatment.
- Less than 50% completing at least one follow-up telephone call.

All major protocol deviations will be reported in the primary report.

Analysis populations

20. Definition of analysis populations

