- All patients with registered preferred gait velocity at 6- and 12-months follow-up
- Withdrawals/lost to follow-up with reasons and timing for both treatment arms
- Patients included in the ITT and per protocol for both treatment arms

Baseline patient characteristics

- 25a: List of baseline characteristics to be summarized

Baseline data that will be presented include: Age, gender, duration of dizziness, education level, reported employment status, number of dizziness complaints, reported weekly activity level. In addition will primary and secondary outcome scores at baseline be presented.

For further details, please see the published study protocol (1).

- 25b: Details on descriptive summary of baseline characteristics

Categorical and binary data will be summarized by absolute and relative frequencies. Continuous and count data will be summarized by mean and median with standard deviation and percentiles as appropriate. In case of only few different values observed or unusual shape of the distribution (e.g. bimodality, extreme skewness), also absolute and relative frequencies will be reported, potentially after a suitable categorization. No formal tests for significant differences between groups at baseline will be performed, as this is not recommended by CONSORT.

SECTION 6. ANALYSIS

Outcome definitions

- 26. Specification of outcomes and timing.

Table 1 presents an overview of the outcomes and timing. A detailed presentation of the primary outcomes is presented in section 3, while the secondary outcomes are presented in the study protocol (1).

Analysis methods

- 27. What analysis methods will be used

All outcomes will be presented using descriptive statistics; normally distributed data by the mean and standard deviation (SD), and skewed distributions by median and interquartile range (IQR). Binary and categorical data will be presented using *counts* and percentages.

Primary outcomes:

The efficacy analysis will be based on the assessment of the between group differences in changes in DHI scores and preferred gait velocity at 6- and 12-month follow-up. A linear-mixed model with repeated measures will be applied, where group allocation (TREATMENT and CONTROL) and time (6 and 12 months) will be treated as categorical values. The estimated difference in change will be presented in group means and 95% confidence intervals with associated p-values.

Secondary outcomes

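### The plan does not say how the 6- and 12-month visits enter the Holm-Bonferroni family, so the contrast that decides the trial is undefined; if either visit can carry the claim, family-wise error exceeds 5%

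*Combined protocol and SAP*

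**What the plan says.** Section 9 states "The study has two primary outcomes", the DHI and preferred gait velocity, and defines the primary endpoints as the group difference in change of handicap and "preferred gait velocity from baseline to 6 and 12 months follow up". Section 27 repeats both visits for the efficacy analysis: "between group differences in changes in DHI scores and preferred gait velocity at 6- and 12-month follow-up". For the model it says "A linear-mixed model with repeated measures will be applied", with group and time (6 and 12 months) as categorical terms, and for reporting "The estimated difference in change will be presented in group means and 95% confidence intervals with associated p-values".

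The error rate is set in section 16, where tests "will consist of two-sided tests with a 95% confidence level", and in section 17: "Since this study has two primary outcomes post-hoc analysis the Holm-Bonferroni method will be used to control for a possible Type 1 error". Section 17 does not mention visits. Nowhere do the documents name a deciding visit, a joint or averaged test, a requirement that both visits succeed, or a rule for declaring success.

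**The concern.** Two outcomes at two visits can give four primary contrasts, and the only reason given for adjustment is that there are two outcomes. The natural way to apply such a rule is to run Holm over DHI and gait velocity at each visit. The second visit then goes unadjusted, and each outcome has two chances to succeed.

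What is at stake is the meaning of the primary result. If one visit is significant and the other is not, the SAP does not say whether superiority was shown. The blinded interpretation step in sections 10 and 32 does not close this gap: the authors agree their interpretation after seeing the A-versus-B results, so a deciding contrast chosen then is chosen with the results in view. Calling the adjustment post-hoc adds to the doubt about what was fixed in advance.

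**Working it through.** **Inputs from the documents.** Two-sided 0.05 (section 16); Holm, justified by two outcomes (section 17); two visits (sections 9 and 27); the design figures in section 11.

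**Assumptions, not in the documents.** Correlation between the 6- and 12-month contrasts, varied from 0 to 1; correlation between the two outcomes, varied from 0 to 0.5.

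**1. The plan's own figures.** n per group = 2(z₀.₉₇₅ + z₀.₈₀)² SD²/δ², with (1.960 + 0.842)² ≈ 7.849.

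- DHI, for "a clinically important group difference in the DHI of 11 points" and SD 18.95: 2 × 7.849 × 18.95²/11² = 46.6, so 47.
- Gait velocity, 0.1 m/s and SD 0.15: 2 × 7.849 × 0.15²/0.1² = 35.3, so 36.
- Drop-out: 94/(1 − 0.24) = 123.7, so 124.

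All three reproduce. The sizing treats each outcome as one comparison at 0.05 and names no visit.

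**2. Error if Holm is run at each visit and either visit suffices.** At each visit the smaller of two p-values must reach 0.05/2 = 0.025. With no effect anywhere, a false claim occurs when any of the four p-values is at most 0.025. If all four are independent, this is 1 − 0.975⁴ = 9.63%. With correlation, from 1,000,000 simulated sets of four z statistics per scenario, counting rejections in either direction:

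| 6/12-month correlation | outcomes independent | outcome correlation 0.3 | outcome correlation 0.5 |
|---|---|---|---|
| 0.5 | 9.14% | 8.90% | 8.49% |
| 0.6 | 8.76% | 8.62% | 8.27% |
| 0.7 | 8.43% | 8.25% | 7.88% |
| 0.8 | 7.87% | 7.73% | 7.43% |
| 0.9 | 7.12% | 6.93% | 6.66% |
| 1.0 | 4.93% | 4.87% | 4.65% |

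If one outcome truly differs and is rejected at both visits, Holm tests the other at 0.05 at each visit. With independent visits the error is 1 − 0.95² = 9.75%, the largest value found over the correlations considered. It is 9.1% at a correlation of 0.5 and 8.3-8.4% at 0.7.

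**3. Error under other readings.**

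- One contrast per outcome (averaged over visits, one named visit, or a joint test), Holm over two: 1 − 0.975² = 4.94% if the outcomes are independent; 4.6-5.0% over the outcome correlations considered.
- Holm over all four p-values (first step 0.05/4 = 0.0125): 1 − 0.9875⁴ = 4.91% if independent, and lower with positive correlation.
- Both visits required for an outcome: about 0.7-1.4% at between-visit correlations of 0.5-0.7, with no effect anywhere.

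**4. Power at each first step.** Normal approximation: power = Φ(δ/(SD√(2/n)) − z₁₋α/₂). For DHI, δ/(SD√(2/n)) is 2.814 with 47 per group and 3.232 with 62 per group (124/2, no drop-out).

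| first step | DHI, 47 | DHI, 62 | gait, 47 | gait, 62 |
|---|---|---|---|---|
| 0.05 (as sized) | 80% | 90% | 90% | 96% |
| 0.025 | 72% | 84% | 84% | 93% |
| 0.0125 | 62% | 77% | 77% | 89% |

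**The case against.** A reader might infer that the plan's family-wise error simply is 8-9% instead of 5%. The documents do not support that. The figure needs three things they do not state: that Holm is run separately at each visit, that success at either visit is enough, and a between-visit correlation of roughly 0.5-0.8.

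The case for the plan goes further.

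- Section 17 gives a reason for using Holm but not the number of p-values in it. Holm over all four is compatible with the text.
- Section 27 lists group and time as model terms and writes no group-by-time interaction, while section 20 treats the primary outcomes as change scores. Taken literally, that model has one group effect per outcome, averaged over the visits, for which a two-outcome Holm is correct. Section 27 also speaks of the difference in change in the singular.
- The stated hypothesis couples the gain in handicap with a gain in gait velocity. If both outcomes had to succeed, a false claim under no effect at all would be rare. Inflation could still arise when only one outcome truly differs.

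All of this stands as a reason not to call the inflation proven. It does not remove the ambiguity. Sections 9 and 27 both name the two visits, none of the protective readings is written down, and a joint reading of the hypothesis fits poorly with Holm, which lets either outcome succeed alone.

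**Conclusion.** The concern holds as a gap in the definition of the primary test. Two outcomes are primary at two visits, the multiplicity rule is justified by the outcomes alone, and nothing says how the visits enter the family or which contrast decides.

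The size is conditional. Under per-visit Holm with success at either visit, the error is about 8-9% at an assumed 6/12-month correlation of 0.5-0.8 when the outcomes are independent or weakly correlated (down to 7.4% at 0.8 if they correlate at 0.5). It is 7.1% at a visit correlation of 0.9 with independent outcomes, and at most about 9.75%. It falls to 5% only as the visits become perfectly correlated. Under one contrast per outcome, or Holm over all four p-values, 5% is kept. A plan that admits readings from about 1% to nearly 10% has not fixed its type I error.

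**What to change.** Before any A-versus-B results are seen, amend sections 17 and 27 as follows.

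1. Name one contrast per outcome on which Holm acts: for example the group difference in change averaged over 6 and 12 months, or the difference at one named primary visit. Write the model terms that produce it, including whether a group-by-time term is fitted.
2. Report the visit-specific differences with 95% intervals as supportive.
3. State what counts as success: either outcome, or both.
4. Delete the term post-hoc from section 17.

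This changes SAP wording only. The cost is that a result at a single visit can no longer be claimed as primary on its own, unless that visit is the one named. The first Holm step stays at 0.025, as a two-outcome Holm already implies.

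If separate claims at 6 and 12 months are wanted, run Holm over all four p-values and say so. That also controls the error, but the first step falls to 0.0125, where DHI power is about 62% with 47 per group and 77% with 62, against the planned 80%. Reaching 80% at that step would take 67 per group for DHI and 51 for gait velocity. The single-contrast option is therefore the cheap one.

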The overall goal for this study is to evaluate the efficacy of a group-treatment integrating VR and CBT (TREATMENT group), compared with a tailored home-exercise program with telephone follow-up (CONTROL group) in persons with persistent dizziness.

Hypothesis:

Participants receiving the Vestibular Rehabilitation and Cognitive Behaviour Therapy (VR-CBT) programme will show significantly superior reduction in perceived dizziness related handicap in addition to increased preferred gait velocity, compared with persons completing a home-exercise program with telephone follow-up.

SECTION 3: TRIAL METHODS

9. Brief description of trial design

The study is designed as an assessor-blinded randomised controlled superiority trial with a two-group parallel design. All participants received a brief Intervention Vestibular rehabilitation session (BI-VR) (see study-protocol (1)) before being randomised, using block randomisation (with 16 participants in each block), into either CONTROL (home-exercises) or TREATMENT (VR-CBT) group.

All included participants went through baseline assessment comprising physical examination outcome measures and self-reported questionnaires. Prior to randomisation all participants received an individual one-hour BI-VR session with a physiotherapist. The session included physical examination, information regarding the vestibular system and possible causes of dizziness, advice related to findings, all with the intention of reducing fear of movement. In

addition, the participants were supervised in selected VR exercises related to their complaints. All participants were advised to be active. After the BI-VR session, the participants were randomised into a CONTROL or TREATMENT group.

The participants allocated to CONTROL were encouraged to work with the exercises prescribed by the BI-VR physiotherapist, and to stay active. The physiotherapist offered two telephone consultations during a 4-month period to encourage compliance with home-exercises and answer questions that may have arisen.

The participants allocated to TREATMENT group attended a structured group-treatment program (VR-CBT). Each group included five to eight participants attending weekly group sessions for 8 weeks. Each session lasted 2 hours and was led by two physiotherapists, integrating VR and CBT following an established treatment manual.

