Intention-To-Treat: Primary analyses will be conducted according to intention to treat protocol, where all participants were included according to the treatment group they were randomized into. The distribution of the primary outcomes (change score of DHI and preferred gait velocity) will be visualized using scatterplots and described by mean and 95% CI for each group.

Per protocol: In addition, analyses will be conducted on the two groups with respect to treatment adherence (See definition of good adherence section 19a). Thus, analyses will be conducted using per protocol analysis, according to this comparison:

- Participants in the CONTROL group with good adherence, and no other interventions.
- Participants in the TREATMENT groups with good adherence, and no other interventions.

SECTION 5: TRIAL POPULATION

Screening data

- 21. Reporting of screening data

The total number of possible participants screened for eligibility throughout the recruitment period (start and end date) will be reported.

Eligibility

- 22. Summary of eligibility criteria

Inclusion criteria:

- 18-70 years
- Acute onset of dizziness, with symptoms lasting at least 3 months
- Dizziness triggered/ worsened by head movements

Exclusion criteria:

- Self-reported non-vestibular reason for dizziness (e.g. neurological condition)
- Fluctuating vestibular disease (e.g. Menière's disease)
- Recently treated or organised future treatment for benign paroxysmal positional vertigo (1 month previously or in the future).
- Conditions where fast head movements are contraindicated (e.g. osteoporosis of the neck)
- Severe/ terminal pathology
- Participation of group therapy for dizziness in within the past year

- Inadequate Norwegian language proficiency (written and oral)
- Unable to attend test and treatment location.

Recruitment and withdrawals

- 23 & 24: Information to be included in the CONSORT flow diagram

The CONSORT flow diagram will consist of the following:

- All patients assessed for eligibility throughout the recruitment period
- All patients meeting one or more of the exclusion criteria, with reasons
- All patients eligible for inclusion in the trial
- All eligible patients not consenting, with reasons
- All patients randomized for both treatment arms
- All patients receiving and not receiving the allocated treatment for both treatment arms
- All patients with answered DHI questionnaire at 6- and 12-months follow-up

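### The per-protocol sets are selected by non-comparable adherence rules, and the major-deviation trigger uses a stricter attendance cut than the adherence definition

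*Combined protocol and SAP*

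**What the plan says.** **Adherence, section 19a.** TREATMENT participants must satisfy two conditions: "attending 6 of the 8 group treatment sessions (75%), and completion of at least 80% of the exercise diaries". The diary scale is demanding, "where 100% was predefined as reporting exercising and following the walking program 5 times per week". For CONTROL, "Satisfactory compliance in the control group was predefined as completion of at least one phone call with the BI-VR therapist (1" (the closing number cites the published protocol). Section 9 gives the context for that call: "The physiotherapist offered two telephone consultations during a 4-month period to encourage compliance with home-exercises".

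**Per-protocol sets, section 20.** ITT is primary. A per-protocol comparison is added, using the 19a definitions, with a second filter worded alike in both arms. For TREATMENT it reads "Participants in the TREATMENT groups with good adherence, and no other interventions".

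**Major deviations, section 19c/d.** Two group-level triggers are listed: "Less than 50% attending more than 75% of the VR-CBT treatment" and "Less than 50% completing at least one follow-up telephone call". Any major deviation must appear in the primary report.

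The documents give no expected adherence rate for either arm and no adjustment for selection in the per-protocol comparison. They do not say how its result is to be interpreted. Section 16 applies two-sided testing at 0.05 to all between-group effects.

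**The concern.** CONTROL's intervention is a home-exercise programme, yet its adherence rule records only contact with a therapist. TREATMENT is filtered on sustained attendance and exercise, and CONTROL is not filtered on exercise at all. If people who persist with a programme also tend to improve more, a strict filter in one arm and a loose one in the other can produce a difference that the treatment did not cause. Nothing in section 20 stops that difference from being tested at 0.05 and offered as support for efficacy.

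The second problem is internal consistency. A participant with exactly 6 sessions meets the attendance criterion in 19a but is not counted among the good attenders in 19c/d. The primary report could then declare a major deviation in a trial where most of the TREATMENT arm attended as much as 19a asks.

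**Working it through.** **1. The two attendance cuts**

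6/8 = 75.0%, as 19a states, and 7/8 = 87.5%. At least 75% is met by 6, 7 or 8 sessions; more than 75% is met only by 7 or 8. This needs no assumption.

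How often the cuts disagree depends on attendance, which the documents do not give. Assume mean attendance of 75% per session.

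- Independent sessions, Binomial(8, 0.75): P(6) = 0.311, P(7) = 0.267, P(8) = 0.100. So P(6 or more) = 0.679 and P(7 or more) = 0.367.
- Clustered attendance, beta-binomial with the same mean and an assumed within-person correlation of 0.3 (a + b = 1/0.3 - 1 = 2.333, so a = 1.75, b = 0.583): P(6 or more) = 0.665 and P(7 or more) = 0.533.
- At correlation 0.2: 0.661 and 0.491.

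The trigger fires when the share falls below 50%. On the 19a cut it would not be expected to fire in any of these cases. On the 19c/d cut it would at correlation 0 (37%) and just would at 0.2 (49%), but not at 0.3 (53%). With independent sessions the two cuts give opposite expected answers for mean attendance between about 68% and 80%.

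**2. Selection in the per-protocol contrast**

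Inputs from section 11: SD of DHI change 18.95, target difference 11 points, 124 participants (62 per arm). Both SD and target reproduce the plan's 47 per group: 2 × (1.960 + 0.842)² × 18.95² / 11² = 46.6, rounded up to 47.

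Assumed, because the documents give neither: the fraction q retained in each arm, and the correlation r between adherence and DHI improvement, taken as equal in both arms.

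Model: each arm keeps the top fraction q on a normally distributed adherence score, and there is no true effect. The mean improvement among those kept rises by r × 18.95 × φ(z)/q, where z is the cut that leaves fraction q above it. The values of φ(z)/q are:

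- q = 0.60: 0.386/0.60 = 0.644
- q = 0.95: 0.103/0.95 = 0.109
- q = 0.80: 0.280/0.80 = 0.350
- q = 0.50: 0.399/0.50 = 0.798

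Spurious difference = r × 18.95 × (TREATMENT value - CONTROL value); positive favours TREATMENT:

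| Retained, TREATMENT v CONTROL | r = 0.2 | r = 0.3 | r = 0.4 |
|---|---|---|---|
| 60% v 95% | 2.03 | 3.04 | 4.06 |
| 60% v 80% | 1.11 | 1.67 | 2.23 |
| 60% v 60% | 0 | 0 | 0 |
| 60% v 50% | -0.58 | -0.88 | -1.17 |

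Example: 0.3 × 18.95 × (0.644 - 0.109) = 3.04. At r = 0 every entry is 0.

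Effect on a nominal 5% test at 60% v 95%, ignoring dropout: SE = 18.95 × √(1/37.2 + 1/58.9) = 3.97. A shift of 3.04 then gives a two-sided rejection rate of about 12%. At r = 0.2 and 0.4 it is 8% and 18%. At 60% v 80% the range is 6% to 8%.

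The other-interventions filter is not in this table. If it removed 10-20% of CONTROL, mainly the least improved (assumed r of 0.3-0.5), CONTROL's mean improvement would rise by 1.1-3.3 points, which could offset part or all of the bias.

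**The case against.** **Direction and size are not documented.** A reader might infer that almost all of CONTROL enters the per-protocol set, so that the comparison must favour TREATMENT. The documents do not support this. No call-completion rate is given, 19c/d provides for fewer than half completing a call, and one call is not enough for entry because other interventions also exclude. The sign depends on TREATMENT keeping the smaller fraction and on adherence tracking improvement. The model also lets answering one call predict improvement as strongly as attending sessions and keeping diaries, which is doubtful. This objection stands against any single figure or a certain direction. It does not make the two sets comparable.

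**The trigger may not misfire.** A reader might infer that it will fire wrongly. That depends on how attendance clusters: at within-person correlation 0.3 it would not be expected to fire at 75% mean attendance. Nor is someone with 6 sessions fully adherent under 19a, which also requires diaries. Both points stand, so the claim is limited to attendance. The conflict between the two cuts remains.

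**The consequences are limited.** ITT is primary, and section 32 has the blinded interpretations agreed on ITT results. The flow diagram (sections 23 and 24) shows per-protocol numbers by arm, and 19b reports attendance and home exercise separately, so unequal retention will be visible. The trigger prompts reporting and defines no population. All of this stands and limits the severity. Visibility does not remove the bias, though, and no section labels the per-protocol result as descriptive.

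**Conclusion.** The concern holds in two limited parts.

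First, the per-protocol sets are selected after randomisation by criteria that do not correspond between arms, so the contrast is open to selection bias. The probable direction favours TREATMENT, because its rule is much the stricter, but this is a judgement and not a documented fact. Over the assumed retention pairs and correlations above, the bias runs from about -1.2 to +4.1 DHI points, against a target difference of 11. It is zero if adherence is unrelated to improvement, or, in this model, if both arms retain equal fractions.

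Second, the attendance cuts in 19a and 19c/d conflict, as a matter of arithmetic. Whether the conflict changes what is reported depends on attendance, for which the documents give no figure.

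The primary ITT analysis is untouched by either part. Both are worth correcting because the corrections cost almost nothing.

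**What to change.** 1. In 19c/d, change *more than 75%* to *at least 75% (6 of 8 sessions)*, so that the trigger matches the attendance criterion in 19a.
2. In section 20, state that the per-protocol contrast is descriptive: estimate and confidence interval, no p-value, and not used as support for efficacy.

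The cost is two small edits to the SAP, with no new data and no change to the primary analysis.

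Optional: add a complier-average estimate that uses randomisation as the instrument, preferably with number of sessions attended as the exposure. Its interval is wider, and it assumes that assignment acts only through attendance. Cutting attendance at 6 sessions would add the assumption that 1-5 sessions do nothing, which is why the count is preferable. This is a trade-off for the sponsor to weigh, and the two edits stand without it.
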